9. RESEARCH METHODS

9.1 STUDY DESIGN

This study will be a retrospective cohort, descriptive study of patients with idiopathic pulmonary fibrosis (IPF). Patients with IPF who initiated either pirfenidone or nintedanib between October 2014 to September 2021 will be identified. The study will use data from the Optum Research Database (ORD), a claims database containing approximately 14 million commercial enrollees and 4 million Medicare-advantage enrollees. The date of the first prescription of either pirfenidone or nintedanib will be assigned as index date. Two separate cohorts will be created - 1) pirfenidone initiators, and 2) nintedanib initiators, and all outcomes will be assessed in the 12 months post-index period. A 12-month time-period prior to the index date will be used as the baseline period for determining the characteristics of patients in both cohorts. To allow for a 12-months baseline and follow-up periods for all patients, the span of data will be from 10/01/2013 to 09/30/2022. (Figure 1)

[figure not shown]

Figure 1 Study Design Schematic

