The main outcome of our study will be incidence of dose reduction/interruption, calculated separately for pirfenidone and nintedanib. For each patient, average daily dose will be calculated in pre-specified time-periods (for example – the first 6 months, the first 12 months, and the average daily dose calculated separately in each month since drug initiation) (more details in section 2.6). Incidence of dose reduction/interruption will be defined as average daily dose not following the prescribing information (PI). According to the PI, the daily dose of pirfenidone is 2403 mg [13], hence the study will consider average daily dose less than 2165 mg (90% of PI dose) as dose reduction for pirfenidone [12]. For nintedanib, the daily dose allowed under prescriber information is 200 mg [14], hence less than 200 mg will be considered a dose reduction for nintedanib patients. As a secondary outcome, we will also assess drug discontinuation during first 6 and 12 months separately for pirfenidone and nintedanib and will be defined as a gap of at least 60 days in filling of prescription (a gap of 60 days after the prescription date + days of supply for the current prescription). In a sensitivity analysis, we will explore 30- and 90- days gap as a definition for drug discontinuation. As this is a descriptive study, assessment of the dose reduction and discontinuation for both drugs will be considered separately, and only descriptively, without any direct comparison between the two cohorts.

NIS Protocol Page 16 of 36

Study number: 1199-0526 Document number: c41847952-01

Proprietary confidential information © 2023 Boehringer Ingelheim International GmbH or one or more of its affiliated companies

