9.2.2 Study population

For the primary study objective, patients included in the cohort need to meet the following criteria:

- Presence of at least one pirfenidone or nintedanib prescription during the identification period (the date of first prescription for pirfenidone/nintedanib is the index date)
- Evidence of IPF: patient with at least one inpatient or two outpatient claims (>14 days apart) with a diagnosis code for IPF (ICD-10-CM: J84.112; ICD-9-CM: 516.31) during the study period (10/01/2013 to 09/30/2022)
- At least 18 years old at the index date
- Have at least 12 months of continuous enrollment in the health plan during pre-index period, and at least 6 months of continuous enrollment in post-index period (for 12-months analysis, patients would be required to have 12 months post-index continuous enrollment)

Exclusion criteria include the following:

- Any history of lung transplant during the 12-months pre-index/baseline period
- Any claims for a skilled nursing facility, a long-term care facility or hospice care during the 12-month pre-index period
- Evidence (≥2 ICD-9-CM or ICD-10-CM diagnostic codes on different dates) of non-IPF chronic fibrosis ILD or connective tissue diseases during the 12-months pre-index period. The following conditions will be excluded: autoimmune, or connective tissue diseases (i.e., rheumatoid arthritis (RA), systemic lupus erythematosus (SLE), dermatopolymyositis, systemic sclerosis, Sjogren's syndrome, and mixed connective tissue disease (CTD)), sarcoidosis, and hypersensitivity pneumonitis).
- Missing demographic information (i.e., age or sex)

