9.3.2.2 Secondary outcomes

We will assess drug discontinuation as a secondary outcome. Pirfenidone or nintedanib discontinuation will be defined as presence of sixty or more days gap in refilling a prescription of the drug (sixty days gap counted from the date of last fill plus the days of supply for the fill). The date of last fill plus the days of supply for the fill (typically 30 days) will be designated as date of discontinuation, and time to discontinuation will be calculated as time between date of discontinuation and index date (only for patients who discontinue the drug). We will calculate the percentage of patients who discontinue each drug in first 6- and 12-months post-index period. As a sensitivity analysis, we will calculate drug discontinuation using 30 days and 90 days as allowed gap between the scripts (vs. 60 days)

We will also assess how many patients initiate either of the antifibrotic drugs (including the same drug the patient has discontinued) during the follow-up time post discontinuation of their index drug. We will separately assess initiation of the index drug vs. initiation of the other antifibrotic agent.

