9.7 DATA ANALYSIS

9.7.1 Main analysis

Baseline characteristics for the pirfenidone and nintedanib cohorts will be reported as frequencies with percentages for categorical data, and means with standard deviations (SD), and median with interquartile range will be reported for continuous variables. We will compare the baseline characteristics using Student's T-test or Wilcoxon rank-sum test for continuous variable, and chi-square test for categorical variable

Average daily dose during first 6 months and 12 months after drug initiation will be reported as means with standard deviations (SD), and median with interquartile range. Six months and 12-months daily dose categories will be presented as frequencies with percentages. Incidence of dose reduction will be reported by month of occurrence (using month 2 and onwards) and reported as frequencies with percentages. Time to drug dose reduction will be reported in months (mean (SD)). Drug discontinuation will be reported as frequencies with percentages, and time to drug discontinuation will be reported in months (mean (SD)). As this is a descriptive study, there will be no multivariable adjustment and/or direct comparison of outcomes between the pirfenidone and nintedanib cohort.

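### No rule lets claims after month 12 confirm a stop dated within it; followed as written, stops after about day 305 go uncounted

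*Combined protocol and SAP*

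**What the plan says.** Section 9.3.2.2 defines discontinuation by a gap without refill: "sixty days gap counted from the date of last fill plus the days of supply for the fill". The event is then dated back to the start of that gap: "The date of last fill plus the days of supply for the fill (typically 30 days) will be designated as date of discontinuation". The results are a percentage and a time: "We will calculate the percentage of patients who discontinue each drug in first 6- and 12-months post-index period". Mean time is taken over discontinuers only. Section 9.7.1 repeats this: "Drug discontinuation will be reported as frequencies with percentages, and time to drug discontinuation will be reported in months". For sensitivity, Section 9.1 adds "we will explore 30- and 90- days gap as a definition for drug discontinuation".

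Three places set the length of follow-up:
- Section 9.1: "all outcomes will be assessed in the 12 months post-index period". The data span there is sized for 12 months after the last index month.
- Section 9.2.2: "for 12-months analysis, patients would be required to have 12 months post-index continuous enrollment". For the 6-month analysis the minimum is 6 months.
- Section 9.3.2.1, under average daily dose, ends each patient's follow-up at discontinuation or at 12 months, and says this holds for all calculations.

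No section says whether claims after month 12 may complete a gap that began before it, how a gap still open at day 365 is classified, or what happens when enrollment ends in mid-gap.

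**The concern.** A stop is dated at the start of the gap but becomes known only when the gap has run its length. If observation ends at day 365, the last weeks of the window can never yield a stop, and patients who stopped then are counted as persistent.

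Four results would be affected:
- The 12-month discontinuation percentage, half of the secondary aim, would be too low.
- Mean time to discontinuation would be too short, because the late stops are the ones missed.
- The 30-, 60- and 90-day results would differ partly because the countable window shrinks as the gap lengthens. A reader would take this for sensitivity to the definition.
- A patient with an open gap at day 365 would enter the subgroup that never discontinues (Section 9.3.2.1), with an average daily dose lowered by the untreated days.

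The study is descriptive, so these percentages are the result itself, and no later step corrects them.

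**Working it through.** The plan states no discontinuation risk or event count, so there is no figure of its own to reproduce.

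**Inputs from the protocol.** Window W = 365 days (Sections 9.1, 9.2.2). Gap g = 60 days, with 30 and 90 for sensitivity, and a typical supply of 30 days (Section 9.3.2.2). Index dates October 2014 to September 2021 (Section 9.1), which is 2,557 days. Data end 30 September 2022 (Sections 9.1, 9.4).

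**Assumed.** True 12-month risk p = 20-60%. Hazard shape k = 1 (constant), or 0.7 and 0.5 (stops clustered early). Share q enrolled for the whole gap after day 365 = 95, 90 or 80%. Index dates evenly spread. No one restarts.

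**1. Last confirmable stop.** A gap starting on day D is complete on day D + g, so without later claims D can be at most W - g:
- 30-day gap: 365 - 30 = day 335
- 60-day gap: 365 - 60 = day 305
- 90-day gap: 365 - 90 = day 275

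These limits need no assumed risk.

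**2. Undercount if no later claims are used.** Let F(t) = 1 - exp(-λ(t - 30)^k), with λ set so that F(365) = p. The reported figure is F(365 - g). For k = 1, p = 0.4, g = 60: 1 - 0.6^(275/335) = 34.25%, a relative loss of (40 - 34.25)/40 = 14.4%.

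| k | Reported at p = 40%, gap 30/60/90 | Spread, points | 60-day relative loss at p = 20/40/60% | Mean months to stop at p = 40%, full window vs cut at day 305 |
|---|---|---|---|---|
| 1 | 37.2 / 34.3 / 31.2% | 6.0 | 16.3 / 14.4 / 11.9% | 6.0 vs 5.2 |
| 0.7 | 38.0 / 35.9 / 33.7% | 4.4 | 11.7 / 10.2 / 8.4% | 5.0 vs 4.4 |
| 0.5 | 38.6 / 37.0 / 35.4% | 3.2 | 8.5 / 7.4 / 6.0% | 4.2 vs 3.7 |

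Because no one restarts in this model, all three definitions would give 40% with full run-out. The spread therefore comes from the window alone.

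**3. Loss if later claims are used.** Loss = (p - F(365 - g)) × (1 - q(1 - g/2557)). For k = 1, p = 0.4, g = 60, q = 0.95: 5.75 × (1 - 0.95 × 0.9765) = 0.42 points. For q = 95/90/80%:
- 30-day gap: 0.17 / 0.31 / 0.59 points
- 60-day gap: 0.42 / 0.70 / 1.26 points
- 90-day gap: 0.74 / 1.16 / 2.01 points

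This slightly overstates the loss, since a stop on day 310 needs only 5 days beyond day 365.

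**4. Effect on average daily dose.** Take a full-dose patient whose supply ends on day 320 and who never refills. If the stop is recognised, the denominator is 320 days and the average is 100%. If not, it is 320/365 = 87.7%, and the patient drops from the top dose category of Section 9.3.2.1 to the next.

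**5. Six months.** With 183 days, a gap that starts at the end of the window is complete by day 243 (60-day gap, about 8 months) or day 273 (90-day gap, about 9 months). Both fall inside 12 months, so only patients whose enrollment ends before then are affected.

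**6. Available run-out.** With data to 30 September 2022, index dates through 31 August, 1 August and 2 July 2021 have full run-out for the 30-, 60- and 90-day gaps. The share of index days without it is 30/2557 = 1.2%, 60/2557 = 2.3% and 90/2557 = 3.5%. Section 9.2.1, however, gives the current data end as 30 September 2021. On that date, index dates after 30 September 2020 would lack even 12 months of follow-up.

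**The case against.** The best reply is that Section 9.1 may limit only the date of the stop. A stop dated day 330 lies within the first 12 months by the wording of Section 9.3.2.2. The enrollment period in Section 9.2.2 is a minimum for inclusion, not a cap on the claims used, and Section 9.4 takes claims to the end of availability. A sensible programmer would look ahead, and step 3 shows that little is then lost. This stands as an argument about size. It does not supply the rule: the 12-month data span in Section 9.1 and the censoring sentence in Section 9.3.2.1 favour a hard stop at 12 months, and even with look-ahead a patient who leaves the plan in mid-gap has no defined status. The censoring sentence sits under average daily dose, so whether it governs discontinuation is itself unclear.

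It is also fair that the size rests on assumed risks, hazard shapes and enrollment shares. Only the day limits follow from the protocol alone.

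A reader might go further and infer that the 6-month figure is understated across the whole cohort (under constant hazard and 40% 12-month risk, 20.7% falling to 13.1%). The documents do not support this. Outcomes are assessed over 12 months, so claims up to month 12 can confirm a 6-month stop wherever enrollment lasts.

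A reader might also extend the point to sustained dose reduction, which must last 60 days. There it is a minor edge effect, confined to onset in month 12.

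**Conclusion.** The point holds and should be fixed before the analysis database is built. The protocol lets an event be dated inside a 12-month window that is, as written, too short to confirm it. Without later claims, the 60-day relative undercount at 12 months is about 6-16% over assumed risks of 20-60% and the three hazard shapes. At 40% risk, the window alone puts 3.2-6.0 points between the 30- and 90-day results. With later claims, the 60-day loss at 40% risk and constant hazard is about 0.4-1.3 points under 80-95% continued enrollment. At 6 months the problem is limited to patients enrolled for less than about 8 months (9 for the 90-day gap).

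It would be too strong to conclude that the plan forbids later claims or that the larger bias is certain. No section bars their use, and which size applies depends on a choice that the protocol leaves to the programmer.

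**What to change.** - In Sections 9.3.2.2 and 9.7.1, state that the stop date must fall within 6 or 12 months and that claims after the window are used to confirm the gap.
- Censor each patient at the earlier of end of enrollment or end of data, minus the gap length. Disenrollment is then not counted as a stop, and unconfirmable time is not counted as persistence.
- Estimate 6- and 12-month discontinuation for each gap definition by a method that allows for this censoring, for example Kaplan-Meier. A simple percentage no longer suffices once censoring times differ.
- Align the censoring sentence in Section 9.3.2.1 with this rule, so that the dose denominator and the never-discontinue subgroup use the same stop.
- Reconcile the data end date between Section 9.2.1 and Sections 9.1 and 9.4.

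The cost is protocol wording and one extra derivation. No patient is excluded: everyone in the 12-month cohort still contributes to at least day 335, 305 or 275 for the 30-, 60- or 90-day gap. The downside is incomplete run-out for the latest index dates, about 1-4% of index days if data end on 30 September 2022 and index dates are evenly spread.

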9.2.3 Study visits

Not applicable

9.2.4 Study discontinuation

Not applicable.

9.3 VARIABLES

9.3.1 Exposures

There is no primary exposure in this study, as this is a descriptive study evaluating dose reduction/interruption, and drug discontinuation in pirfenidone and nintedanib initiators, separately. There is no direct comparison between the two cohorts (more details in Section 9.7)

NIS Protocol Page 18 of 36

Study number: 1199-0526 Document number: c41847952-01

Proprietary confidential information © 2023 Boehringer Ingelheim International GmbH or one or more of its affiliated companies

9.3.2 Outcomes

9.3.2.1 Primary outcome

The main outcome measure of our study is the incidence of dose reduction/interruption, calculated separately for each drug. For calculating the primary outcome, we will first need to calculate the average daily dose of pirfenidone and nintedanib after drug initiation (post-index period). Specific details of calculations are —

Average daily dose

Average daily dose for each patient will be calculated by taking the average of total drug intake (tablet strength * number of doses) during the time between index date to the date of drug discontinuation

```
Average \ Daily \ Dose \\ = \frac{\sum_{0}^{n}(Tablet \ Strength*number \ of \ tablets \ in \ a \ Rx \ fill)}{Time \ of \ follow - up \{(Date \ of \ discontinuation) - Index \ Date\}} Where n = number of fills a patient has received for pirfenidone/nintedanib
```

- We will calculate average daily dose of pirfenidone and nintedanib separately for each month in post-index period (month 1 to 12) and will also calculate for cumulative periods of 6 months and 12 months. For all calculations, censoring events will be taken into account, with patient censored at the date of drug discontinuation, or end of 12 months.
- Six and twelve months average daily dose categories For the average daily dose calculations in cumulative periods, we will be dividing the patients in following 4 categories
 - 1) Dose strength less than 50%
 - 2) Dose strength between 51% to 66%
 - 3) Dose strength between 67% to 90%
 - 4) Dose strength above 90%

Incidence of Dose Reduction and/or temporary dose interruption

Once average daily dose is calculated for each month post-index (month 1 to 12), incidence of dose reduction/interruption will be calculated as presence of average daily dose $\leq 90\%$ dose strength (for pirfenidone) or $\leq 66.67\%$ dose strength (for nintedanib), as per the PI [12 – 14]. Patients will be required to have the dose reduction for at least for 60 days, to make sure that the dose reduction is not temporary.

In a sensitivity analysis, we will also evaluate temporary dose reductions, i.e., dose reduced to below the above defined dose strength only for 1 month.

In the primary analysis, patients who reduce their dose in the prior months will be allowed to discontinue the drug in future months (For example, in primary analysis, a patient can reduce their index drug dose in month 2 (i.e. dose below label recommendation for the whole month 2 and 3), and then can discontinue the drug in month 4 (or beyond). We will also evaluate the incidence of dose reduction in patients who never discontinue the index drug.

NIS Protocol Page 19 of 36

Study number: 1199-0526 Document number: c41847952-01

Proprietary confidential information © 2023 Boehringer Ingelheim International GmbH or one or more of its affiliated companies

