7. RATIONALE AND BACKGROUND

Idiopathic pulmonary fibrosis (IPF) is a life-threatening rare disease characterized by decline in lung function due to progression of fibrosis in the interstitium of the lung [1]. In patients with IPF, a decline in forced vital capacity (FVC) is an important indicator of mortality [6]. The median survival of non-treated IPF patients is approximately 3 years from diagnosis [2].

[figure not shown]
Before anti-fibrotic medications became available in the US, IPF treatment mainly consisted of therapeutics that were found not to be of benefit (or even harmful), and a mainstay of care focused on symptom relief and included palliative care [3]. In October 2014, two anti-fibrotic medications, nintedanib and pirfenidone, were approved by the U.S. Food and Drug Administration (FDA) for the treatment of IPF [4, 5], which transformed the treatment of this disease. Both medications were found to reduce the rate of decline in FVC compared to placebo in phase III clinical trials [7, 8].

From the perspective of treatment, the approvals of antifibrotics for IPF were significant breakthroughs. Antifibrotics have demonstrated an ability to slow IPF progression, if taken according to the recommended dosing in the prescriber information and taken continuously, in both clinical trials [7, 8] and real-world evidence [9]. Previous real-world studies have compared persistence/ discontinuation patterns for pirfenidone and nintedanib and found similar persistence patterns for both drugs [10, 11]. However, these studies have failed to consider the differential dosing regimens between these two drugs and corresponding incidence of dose reduction and/or temporary dose interruption. Hence, this study will assess both dose reduction and/or temporary dose interruption and discontinuation patterns for pirfenidone and nintedanib among patients with IPF.

In this study, we will investigate the incidence of dose reduction/interruption beyond the label recommendations (defined as a dose not following the prescriber information (PI), which corresponds to a daily dose of 2165 mg (90% of full dose, which is 2403 mg) for pirfenidone [12, 13] or less than a daily dose of 200 mg for nintedanib (66.67% of full dose, which is 300 mg) [14]) from 10/01/2014 to 09/30/2022 using real-world data. The definition of incidence of dose reduction, which is differential for nintedanib and pirfenidone is because of –

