- 1) In the US, the prescriber information (PI) and/or label for pirfenidone does not indicate any particular dose reduction recommended as per Food & Drug Administration (FDA). For nintedanib, reducing dose from 150 mg to 100 mg BID is part of the PI.
- 2) The post-hoc analysis of clinical trials showed similar slope of FVC decline for patients who reduced the dose to 100 mg BID for nintedanib, but for pirfenidone, the slope of FVC decline was steeper for patients who reduced the dose, potentially indicating that reduced dose might lead to lower benefit on FVC decline (see figures below) [12, 15]

Proprietary confidential information © 2023 Boehringer Ingelheim International GmbH or one or more of its affiliated companies

The current study may be able to demonstrate to decision makers the differential complexities in dosing regimen for pirfenidone vs. nintedanib and may reveal that IPF patients may not be receiving the full benefit of pirfenidone due to possible sub-optimal dosing, even when the patient has not discontinued the drug.

NIS Protocol Page 14 of 36

Study number: 1199-0526 Document number: c41847952-01

Proprietary confidential information © 2023 Boehringer Ingelheim International GmbH or one or more of its affiliated companies

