9.2 SETTING

9.2.1 Study sites

We will use administrative health insurance claims data from the Optum Research Database (ORD) for the period of October 1, 2013 through end of data availability (currently September 30, 2021). The ORD contains enrollment information, as well as fully-adjudicated medical claims and pharmacy claims for commercial enrollees and MAPD beneficiaries. In 2018, the ORD included 14.3 million commercial enrollees with medical and pharmacy benefits and 4.3 million beneficiaries with Medicare Part C (commonly referred to as the Medicare Advantage program). Medicare Advantage beneficiaries choose to receive all of their health care services through a provider organization in lieu of Medicare Part A/B coverage (commonly referred to as Medicare Fee for Service). These plans are referred to as MAPD when combined with Medicare Part D coverage. The average enrollment duration was 31.4 and 37.3 months for commercial enrollees and MAPD enrollees, respectively. Underlying information is geographically diverse across the United States and enrollees are fairly representative of the U.S. population. Medicare beneficiaries retain a single identifier within the system and can be tracked as they change plans, or as they disenroll and reenroll over time.

Claims for pharmacy services are typically submitted electronically by the pharmacy at the time prescriptions are filled. The claims history is a profile of all outpatient prescription pharmacy services provided and covered by the health plan. Pharmacy claims data include drug name, dosage form, drug strength, fill date, days of supply, financial information, and de-identified patient and prescriber codes, allowing for longitudinal tracking of medication refill patterns and changes in medications. Pharmacy claims are typically added to the research database within six weeks of dispensing.

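### The average-daily-dose formula has no rule for supply superseded by a strength change, so a mid-supply step down counts both fills and overstates the dose

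*Combined protocol and SAP*

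**What the plan says.** Section 9.3.2.1 obtains average daily dose by "taking the average of total drug intake (tablet strength * number of doses"). The displayed formula sums tablet strength times tablets per fill and divides by the days from index to discontinuation. The sum runs over every fill: "Where n = number of fills a patient has received for pirfenidone/nintedanib". The dose is calculated "separately for each month in post-index period (month 1 to 12) and will also calculate for cumulative periods of 6 months and 12 months". The cumulative values are then sorted into four dose categories (Section 9.3.2.1) and summarised by mean, SD, median and interquartile range (Section 9.7.1).

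Section 7 describes the nintedanib step down as a change of strength: "For nintedanib, reducing dose from 150 mg to 100 mg BID is part of the PI".

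The plan has no rule that truncates, carries forward or caps overlapping supply, and none that assigns a fill to a month. Days of supply is used only to define and date discontinuation (Section 9.3.2.2), although Section 9.2.1 confirms that the needed fields exist: "Pharmacy claims data include drug name, dosage form, drug strength, fill date, days of supply".

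**The concern.** A step down made by changing capsule strength needs a new fill. If it is dispensed while old capsules remain, the formula counts the unused old capsules and adds the new ones for the same days. In the month of the change, a lower dose is recorded as a dose above full dose, and the cumulative averages carry the surplus forward.

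Average daily dose is named in the primary aim, so it is a reported result as well as a step towards the incidence outcome. The error runs one way: overlap of this kind can only raise the dose, and only in patients whose strength was changed before the supply ended. Because no rule is written, the programmer must choose one, and the choice alone moves the switch-month dose between 250 and 500 mg/day in the example below.

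**Working it through.** **Inputs from the plan.** Nintedanib full dose 300 mg/day and threshold 200 mg/day (Section 7: "200 mg for nintedanib (66.67% of full dose, which is 300 mg"); step down from 150 mg to 100 mg BID (Section 7); typical supply 30 days per fill (Section 9.3.2.2). The plan's thresholds reproduce: 200/300 = 66.67%, and 0.90 × 2403 = 2162.7 mg against the stated 2165 mg (2165/2403 = 90.1%). The plan gives no worked dose example.

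**Assumptions.** 30-day months from index; old capsules unused after the change; new 30-day fills from the day of the change. One 150 mg fill holds 60 × 150 = 9,000 mg and one 100 mg fill holds 60 × 100 = 6,000 mg.

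**Change on day 15, switch month**
- Full content by fill date: (9,000 + 6,000)/30 = 500 mg/day (167% of full dose).
- By days of supply, overlap counted twice: (9,000 + 15 × 200)/30 = 400 mg/day (133%).
- Implied dose: (15 × 300 + 15 × 200)/30 = 250 mg/day (83%).

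So 150 mg/day of the excess is superseded supply (15 × 300/30). The further 100 mg/day under fill-date counting comes from the missing month-allocation rule. A change on day 45 gives the same three figures in month 2. The next two months are 200 mg/day under every method.

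**Change on day 105, 6-month average**
- Full fill content: four 150 mg fills (days 0, 30, 60, 90) and three 100 mg fills (days 105, 135, 165): (36,000 + 18,000)/180 = 300 mg/day (100%).
- Supply clipped at day 180: (54,000 − 15 × 200)/180 = 283.3 mg/day (94.4%).
- Implied dose: (105 × 300 + 75 × 200)/180 = 258.3 mg/day (86.1%).

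Both formula values fall above 90%; the implied dose falls in 67–90%. Of the 41.7 mg/day excess on full content, 4,500/180 = 25.0 is superseded supply and 3,000/180 = 16.7 is supply running past day 180.

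**All mid-supply change days** (174 days in 6 months, 348 in 12 months)

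| Result | Full fill content | By days of supply, clipped |
|---|---|---|
| Switch month above 300 mg/day | all days | all days |
| 6-month average above 300 mg/day | 33% | 25% |
| 12-month average above 300 mg/day | 17% | 12% |
| 6-month category changed | 37% | 25% |
| 12-month category changed | 20% | 12% |

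The cumulative average is overstated for every such day. These are shares of possible change days, not of patients.

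**The case against.** The strongest reply is that the main outcome hardly moves. Section 9.1 counts a nintedanib event only below 200 mg/day ("hence less than 200 mg will be considered a dose reduction for nintedanib patients"), so the labelled step down to exactly 200 mg is not an event there. Section 9.3.2.1 instead uses at or below 66.67%, which would include it; the two passages must be reconciled. Under either definition the implied switch-month dose of 250 mg/day is not an event, and the following months are unaffected, so the nintedanib flag is not lost in this example. That stands. A reader might infer that the formula fails on the incidence outcome itself, and the worked case does not show that.

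A reader might also infer that nintedanib doses are biased upward relative to pirfenidone. The documents do not support this: they give no pirfenidone tablet strengths and do not say how its dose is lowered. If a pirfenidone patient made an early fill at an assumed 1,602 mg/day on day 15, the same double count would give 2403 + 1602 = 4005 mg/day by fill date, or 2403 + 801 = 3204 by days of supply, against an implied 2002.5. That last figure is below the 2165 mg threshold, so a qualifying month would be missed. With the 60-day rule, onset would be delayed by a month, or the event lost near month 12.

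Section 9.9 concedes that fill-based doses may not reflect actual intake. That is a general caution about claims data and does not supply the missing counting rule.

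**Conclusion.** The concern holds for the monthly, 6-month and 12-month average dose and for the dose categories. Under the stated assumptions the switch-month dose is 500 or 400 mg/day against 250, and a day-105 change moves the 6-month average from 258.3 to 283.3 or 300 mg/day and into the top category. A reader might take this to mean that the reduction always appears as an increase. That is certain only for the switch month; most cumulative averages are inflated but stay at or below full dose.

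The documents do not say how often strengths change mid-supply or how much old supply is left, so the cohort-level bias cannot be sized. If unused capsules were in fact taken later, the overstatement would be smaller, but no carry-forward rule is written. The change should be made before programming; it is not a reason to doubt the design.

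**What to change.** In Section 9.3.2.1, for both drugs:

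1. Build a day-by-day supply from each fill (strength × quantity / days of supply), allocate it to months by day, and clip it at the end of each period.
2. When a later fill of the index drug at a different strength is dispensed before the earlier supply ends, end the earlier fill on that date and drop its remaining quantity.
3. Sum different strengths filled on the same date as concurrent use.
4. Report the version that keeps the old supply as a sensitivity analysis; the difference shows how much the rule matters in this cohort.

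With this rule the day-15 example gives 250 mg/day in the switch month, 208.3 over 6 months and 204.2 over 12 months; full fill content gives 500, 250.0 and 225.0.

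The cost is one programming rule on strength, quantity, fill date and days of supply: Section 9.2.1 lists all of these except quantity, which the existing formula already requires. The downside is that some patients may use up old capsules or hold two strengths filled on different dates, so the main result may slightly understate their dose. The rule acts on changes of strength only, so the treatment of early refills at the same strength should be stated beside it.
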